Title:
**Early outcomes of Total Knee Arthroplasty
using the MAKO Surgical Robot and Triathlon Knee**

Principal Investigator:
[name]., M.B.A.

Co-Investigators:
[name]
[name]

Study team members:
[name]
[name]
[name]

OVERVIEW

Background information:

Over 500,000 total knee arthroplasty (TKA) procedures are performed each year in the US and this number is projected to increase to 3.5 million procedures per year by 2030[1]. The vast majority of TKA involve the use manual instrumentation for bone resection, soft tissue balance and prosthesis alignment. Accuracy and precision using these traditional instruments is variable [4]. Improper component placement and instability can increase the risk of failure [5]. Additionally, manual instrumentation predispose to soft tissue damage with poorly controlled saw cuts. Soft tissue trauma may have the potential to increase pain and slow recovery. Furthermore, poorly controlled sawblades may injure critical ligamentous or neurovascular structures. Robotically assisted TKA has been shown to improve surgical accuracy and precision in bone resection, component alignment and soft tissue balance [6]. The avoidance of TKA outliers through the use of robotic assistance has the potential to improve component survivorship. Additionally, the haptic feedback of the robotic arm can prevent sawblade excursion into and damage of soft tissue structures. This may lead to an improvement on postoperative pain and recovery.

Research objectives:

The purpose of this study is to determine the early clinical and radiographic outcomes of robotically assisted total knee arthroplasty with the MAKO surgical robot using the Triathlon knee system. Mean weekly VAS pain score during the first 4 weeks is the primary end point. Results of this study will be compared to prospective cohort of patients in the IRB study 201805014 from this institution who underwent TKA using non-robotic, manual instruments

Primary Hypothesis: Patients receiving robotic TKA will have better early recovery, including lower mean weekly VAS pain score for the first 4 weeks postoperatively and higher functional outcome scores, than the manual TKA historical cohort.

Secondary Hypothesis:

Patients receiving robotic TKA will have more accurate component position and alignment than the manual TKA historical cohort.

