Number of participants: We propose to enroll 95 patients in this prospective cohort. A Pre-hoc power analysis for the primary outcome measure of VAS pain score was performed. The minimum clinically important difference for VAS pain in knee osteoarthritis is reported between 1.5 and 3 in the literature, with a standard deviation of 2 to 3 at one week postoperatively. A medium effect size of 0.5 was estimated using a VAS pain score difference of 1.5 with a standard deviation of 3. With power set at 0.9 and alpha 0.05, power of 0.9, and alpha error of 0.05 were used for the analysis. With these assumptions, 172 patients were required for the study, which includes 86 patients in the current cohort and 86 patients in our historical cohort (data previously collected). Therefore, assuming a 10% drop out rate, we will enroll 95 patients with a goal of achieving 86 patients to match the historical cohort.

Data collection:

Data collection will be done preoperatively, intraoperatively, 3-6 weeks postoperatively and at 12 weeks postoperatively 1 year and up to two year. The data will be analyzed by site staff. All data to be collected can be found in tables 1-7.

All procedures will be performed by two surgeons ([name], [name]) within a single institution at one sites (Barnes Jewish West County).

All participants will undergo standard admission and pre-operative procedure for primary total knee arthroplasty per institution protocol. Participants will be admitted to hospital on day of surgery for elective procedure. PT treatment and evaluation will take place on day of surgery and postoperative day one prior to discharge. Pain medications will be standardized during admission.

Participants will be scheduled for a standard clinical visit at 3-6weeks.

Participants will undergo final evaluation at 3 months post-operatively and beyond.

Focus Motion knee brace app

During the pre-operative arthroplasty class, participants in the sub-study will be set-up with a Fitbit wrist-based activity tracker and FocusMotion knee brace and the appropriate software. Participants will be instructed to use the device in the 2 weeks prior to undergoing surgery, to gather baseline data on narcotic use, pain, use of assistive device and sleep quality. They will continue to use the device for 3 months postoperatively. Patient will keep the software on their phone for up to 2 years.

Subject Payment

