Active Knee ROM	degrees	FocusMotion Brace
Pittsburgh Sleep Quality Index	scale	FocusMotion App Survey
Oxford knee score	scale	FocusMotion App Survey
FJS	scale	FocusMotion App Survey
Visual Analog Scale pain score thigh	scale	FocusMotion App Survey
Visual Analog Scale pain score knee	scale	FocusMotion App Survey
Visual Analog Scale pain score leg/calf	scale	FocusMotion App Survey
% normal knee	Scale	FocusMotion App Survey
Use of assistive device	incidence	FocusMotion App Survey
Narcotic requirement, daily	Daily MME/hr	FocusMotion App survey
Sleep duration	min	Fitbit
Sleep quality (REM sleep/non-REM sleep)	percentage	Fitbit
Sleep disturbances	count	Fitbit
Sleep efficiency(time asleep/time in bed)	percentage	Fitbit
Charleston Comorbidity Index	Score	EPIC CPAP documentation
PROMIS	Score	WUPRO

Table 2: Intra-operative data during procedure

Test	Unit	Collected by
Length of surgery	minutes	Surgeon

Table 3:

Table 3: Post-operative data during hospital stay

Test	Unit	Collected by
Total operative time(skin to skin)	Hours	Chart review
Tourniquet time	Minutes	Chart review
Tourniquet inflation pressures		
Blood loss	mL	Chart review
Occurrence of transfusion	Incidence	Chart review
Time to discharge	Number	Chart review
Total time in hospital	Hours	Chart Review
Pain scores in hospital	Qshift	Chart Review
Morphine equivalents in hospital	mg	Chart Review
PT eval on discharge: distance ambulated, ROM, pain score	Degrees	PT or focus motion brace

Table 4: Daily data points, from postop day 0 to 12 weeks postop

Data	Unit	Collected by
VAS pain score-location of most pain (at the month mark)	Scale	FocusMotion App Survey
Forgotten Joint Score (at the 1 month mark)	Scale	FocusMotion App Survey
% of Normal Knee (a the 1 month mark)	Scale	FocusMotion App Survey
Narcotic requirement, daily	MME/hr	FocusMotion App Survey

Sleep duration	Min	Fitbit
Sleep disturbances	Count	Fitbit
Sleep efficiency (time asleep/time in bed)	percentage	Fitbit
Sleep quality (REM sleep/non-REM sleep)	Percentage	Fitbit
Step count	Count	Fitbit
Use of assistive device	Incidence	FocusMotion App Survey
Active Knee ROM	degrees	FocusMotion Brace
Passive Knee ROM	degrees	FocusMotion Brace
Compliance with home PT protocol	incidence	FocusMotion App

Table 5: Post-operative data at 3 months following procedure

Passive Knee ROM	degrees	Focus Motion Brace
Active Knee ROM	degrees	FocusMotion Brace
PSQI	scale	FocusMotion App Survey
OKS	scale	FocusMotion App Survey
Forgotten Joint Score	scale	FocusMotion App Survey

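### Table 4 contradicts itself on how often post-operative VAS pain is recorded; read literally, its VAS row cannot supply the weekly scores that the primary endpoint needs

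*Combined protocol and SAP*

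**What the plan says.** Research objectives sets the endpoint: "Mean weekly VAS pain score during the first 4 weeks is the primary end point". The Primary Hypothesis uses the same window, expecting "lower mean weekly VAS pain score for the first 4 weeks postoperatively" than in the manual cohort. Data collection then makes the tables the complete schedule: "All data to be collected can be found in tables 1-7".

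Within those tables, the VAS entry for the period after discharge and before 3 months is the first row of the table headed "Table 4: Daily data points, from postop day 0 to 12 weeks postop". That row reads "VAS pain score-location of most pain (at the month mark". The next row reads "Forgotten Joint Score (at the 1 month mark", and the % of normal knee row has a similar note. The row after that is marked daily in its own text: "Narcotic requirement, daily".

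The other pain entries fall outside the gap. Table 3 lists "Pain scores in hospital Qshift Chart Review", which covers the hospital stay. Tables 5, 6 and 7 list VAS at 3, 12 and 24 months. Table 1 lists three pre-operative VAS scores, for thigh, knee and leg/calf.

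**The concern.** A mean weekly score over 4 weeks needs at least one VAS in each of weeks 1, 2, 3 and 4. The one row that could supply these carries a note placing it at the month mark, under a heading that says daily. Staff who build the app survey from the row would collect one VAS near week 4. Staff who build it from the heading would collect one every day. The protocol does not say which is meant.

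At stake is whether the primary hypothesis can be tested as stated. A pain score not asked for in weeks 1-3 cannot be recovered later. Even if scores are collected, the weekly mean and its 4-week summary are not defined, so the analyst would have to choose among possible summaries once data exist.

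**Working it through.** **1. The plan's own figure.** Inputs from Number of participants: difference 1.5, SD 3, alpha 0.05, power 0.90, equal cohorts. The effect size is 1.5/3 = 0.5.

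- Normal approximation: n per cohort = 2(z₀.₉₇₅ + z₀.₉₀)²/0.5² = 2(1.960 + 1.282)²/0.25 = 84.1, rounded up to 85.
- Two-sample t-test (noncentral t): 85.03, rounded up to 86, as stated. Then 86 + 86 = 172. Power at 86 per cohort is 0.903.
- A one-sided test would need 69, so the stated 86 is two-sided.

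The sample size reproduces. What remains is whether the schedule delivers the variable.

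**2. Which part of Table 4 governs the VAS row?**

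- The heading says daily from day 0.
- The row note says the month mark. Two neighbouring rows under the same heading carry a 1-month note and are one-time items within this table. The heading therefore does not govern every row.
- The narcotic row repeats the word daily in its own text; the VAS row does not.
- Tables 5-7 list VAS at the location of most pain as a single scale item. This favours applying the Table 4 note to the whole row and not only to location.

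The row-specific reading is the stronger of the two, but it is not the only one.

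**3. Does any other section fill weeks 1-4?**

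- Table 3: scores every shift by chart review, not called VAS, and ending at discharge. Data collection places discharge after physical therapy on postoperative day one.
- Data collection: the post-operative time points are 3-6 weeks, 12 weeks, 1 year and up to 2 years. None is weekly.
- Focus Motion knee brace app: pain is named among the items gathered in the 2 weeks before surgery. After surgery the text says only that device use goes on for 3 months. Procedures says that platform collection continues. Neither gives a frequency for pain.

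**4. Coverage by week.**

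| Post-operative week | Row note governs | Heading governs |
|---|---|---|
| 1 | In-hospital chart scores only | About 7 VAS |
| 2 | None | About 7 VAS |
| 3 | None | About 7 VAS |
| 4 | One VAS, near week 4 | About 7 VAS |
| Total VAS | 1 | About 4 × 7 = 28 |

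Number of participants takes its SD range (2 to 3) from one week after surgery. On the row reading, no VAS is scheduled between discharge and the end of that week.

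**5. Does the choice of reading change N?** This is an illustration only. Assume that each weekly score has SD 3 and that the four are equally correlated with correlation ρ, which the documents do not give. The SD of the 4-week mean is then 3√((1 + 3ρ)/4).

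| ρ | SD of 4-week mean | n per cohort, 90% power (normal approximation) |
|---|---|---|
| 0.3 | 2.07 | 40 |
| 0.5 | 2.37 | 53 |
| 0.7 | 2.64 | 66 |
| 0.9 | 2.89 | 78 |

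A single VAS with SD 3 needs 85 on the same formula. If the 1.5 difference holds, 86 is enough under either reading.

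**The case against.** The best defence is the heading. VAS is the first row of a table described as daily from day 0, and on that reading the endpoint can be computed with values to spare. The note is also ambiguous in scope, because it follows the words about location and might restrict only that item. Its wording differs slightly from its neighbours, which say 1 month where the VAS row says only month. Finally, the platform gathers pain at baseline and stays in use after surgery, which fits continuing pain capture.

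Much of this stands. A reader might infer that the endpoint simply cannot be computed. The documents do not support that without the condition that the row note governs the score. A reader might also infer that the month mark is the only post-operative VAS, but VAS is also scheduled at 3, 12 and 24 months, and pain scores are charted in hospital. Nor does the narrative say that the app is used daily; it says that device use continues and gives no frequency.

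The defence does not remove the conflict. It needs the heading to override a note on its own row while the same kind of note is honoured on the next two rows. It also points to no sentence that schedules a weekly or daily VAS after discharge.

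**Conclusion.** The point holds as an internal contradiction that bears on the primary endpoint and must be resolved. Table 4 gives two incompatible frequencies for VAS, and no other section settles which applies. If the row note governs the score, which is the better-supported reading, there is one VAS near week 4, weeks 2 and 3 are empty, week 1 has only in-hospital chart scores, and the endpoint cannot be computed as defined. If the heading governs, there are about 28 values and the gap is limited to undefined weekly and 4-week summaries.

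Two further inferences are not supported. One is that the sample size fails: 86 per cohort reproduces and suffices under either reading if the planned difference holds. The other is that a month-1 score would be substituted afterwards: the text leaves room for that but does not say it.

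The conclusion assumes that Tables 1-7 are the full schedule, as Data collection states. The VAS item and timing used in the historical cohort (IRB study 201805014) are not in the documents.

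**What to change.** Reconcile Table 4 with Research objectives:

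- Remove the month-mark restriction from the VAS score and state a frequency that gives at least one VAS in each of post-operative weeks 1-4. Make it daily if the historical cohort was recorded daily. If the note was meant only for the location item, move location to its own row.
- Name the VAS item that forms the endpoint. Table 1 has three site-specific scores, while the post-operative tables use the location of most pain.
- Define the weekly mean and the 4-week summary, for example the mean of each week's entries and then the average of the four weekly means.
- Use the same item and timing as the historical cohort, and state what that cohort recorded. Its data are already collected, so its schedule limits what can be compared.
- State who supplies app-based VAS. The Focus Motion knee brace app section describes device set-up for a sub-study, whereas Procedures describes it for every consented participant.
- Keep the Forgotten Joint Score and % of normal knee at 1 month.

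The cost is a table correction, a short endpoint definition, and one more item in an app survey that already asks daily about narcotic requirement. The added patient burden is small.

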Honorarium of \$100 provided at the 3-6 week post op visit and following completion of the 3 month evaluation. Honorarium of \$50 will be provided once the 1 year and 2 year surveys are completed on the app. Participants in the study will be gifted the FocusMotion smart-brace and platform as well as the Fitbit device

Radiographic Analysis

One standing full length AP and lateral EOS imaging as well as anteroposterior, lateral, and sunrise view radiographs of the knee will be taken preoperatively, and one EOS at one post-op at either 3-6 week visit, or the 3 or 12 month post-op visit in the hospital. Anteroposterior and lateral radiographs will be taken postoperatively in the hospital. The spatial relationship between the native bone and the mechanical axes will be determined and the following angles will be measured: the varus/valgus angle of the femoral component relative to the femoral mechanical axis, the varus/valgus position of the tibial component relative to the tibial mechanical axis, the varus/valgus position of the entire limb as the sum of the tibial and femoral mechanical axes, the extension/flexion of the femoral component in relation to the femoral mechanical axis, the tibial posterior slope, the rotational deviation of the femoral component from the epicondylar axis, and the rotational deviation of the tibial component from the referenced axis. All radiographs will be measured by a blinded independent examiner.

Procedures: Once the participant has signed informed consent, he or she will be setup and instructed on use of the FocusMotion platform and Fitbit device. Data collection will begin 2 weeks preoperatively and will continue for 3 months postoperatively through the focusmotion platform and up to two year. Perioperative data will be collected in the electronic medical record in the hospital. Standard of care office visits with clinical and xray evaluations will be conducted at 3-6weeks, 3 months and beyond.

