Participants Lost to follow-up: Some participants will not return for follow-up at the required intervals. A member of the research team shall contact non-respondent participants using phone calls, regular mail, e-mail, certified letters, or other means to urge participants to return for clinic follow-up or ascertain if a participant has moved, died, or otherwise become lost to follow-up. The following flow chart identifies the steps for attempts to locate lost participants. These actions, along with any other options available to the site, should be followed to exhaust all reasonable means in locating lost participants. These actions should be documented in the participant's records and may be performed concurrently or in parallel.

Phone call to last known number → Contact → Follow-up with participant
↓
No Contact
↓
Phone call to other numbers (spouse, relative, etc.) → Contact → Follow-up with participant
↓
No Contact
Note: There will be a minimum of 10 calls to different numbers at different times of the day, on different days of the week, and over at least 2 weeks
↓
Mail letter to last known patient address → Contact → Follow-up with participant
↓
No Contact
↓
Mail letter to secondary addresses → Contact → Follow-up with participant
↓
No Contact
↓
Mail "certified" type of letter to last address and any secondary address → Contact → Follow-up with participant
↓
No Contact
↓
Social Security Death Index to determine if participant has died → Confirm death
↓
Not Confirmed

End attempts.

INFORMED CONSENT

Written informed consent will be obtained from each participant prior to screening and enrollment. Patients who are identified by the treating surgeon during their clinical office visit as being eligible and who will be scheduling a total knee arthroplasty will be offered participation in the study. The study coordinator will review the informed consent document and study requirements with the patient and answer any questions the patient may have in a private clinic area. The patient will have the opportunity to review the consent form, discuss with family/friends, and do his/her own research on the participant if desired. Once the patient has consented and signed the informed consent, he or she will be screened for eligibility and enrolled on study if eligibility is confirmed.

PROCEDURES FOR MAINTAINING CONFIDENTIALITY

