% of normal knee	Scale	Focus Motion App Survey
VAS pain score (location of most pain)	scale	FocusMotion App Survey
Use of assistive device	incidence	FocusMotion App Survey
Narcotic requirement	daily MME/hr	FocusMotion App Survey
Sleep duration	min	Fitbit
Sleep disturbances	count	Fitbit
Sleep efficiency (time asleep/time in bed)	percentage	Fitbit

Sleep quality (REM sleep/non-REM sleep)	percentage	Fitbit
Wound complications	incidence	EPIC documentation
DVT/PE	incidence	incidence
Infection	incidence	EPIC documentation
Return to OR	incidence	EPIC documentation

Table 6: Post-operative data at 12 months following procedure

PSQI	scale	FocusMotion App Survey
OKS	scale	FocusMotion App Survey
Forgotten Joint Score	scale	FocusMotion App Survey
% of normal knee	Scale	Focus Motion App Survey
VAS pain score (location with the most pain)	scale	FocusMotion App Survey

Table 7: Post-operative data at 24 months following procedure

PSQI	scale	FocusMotion App Survey
OKS	scale	FocusMotion App Survey
Forgotten Joint Score	scale	FocusMotion App Survey
% of normal knee	Scale	Focus Motion App Survey
VAS pain score (location with the most pain)	scale	FocusMotion App Survey

REFERENCES

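### Post-discharge complications rest on EPIC alone for three of four items, with no patient-reported question, so events treated elsewhere or in non-returners may be missed and the robotic rate understated

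*Combined protocol and SAP*

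**What the plan says.** Under G1. Tables, Table 5 (3 months) has four complication rows. Wound complications, infection and return to OR are each collected from "EPIC documentation". The DVT/PE row repeats its unit, incidence, where the source should stand.

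These four rows are the only post-discharge complication data. Table 4 covers day 0 to 12 weeks with app, brace and Fitbit items but no complication item. "Table 6: Post-operative data at 12 months following procedure" and the matching 24-month table list survey scores only. The Data collection section says that Tables 1 to 7 hold everything to be collected.

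On contacts, the same section states: "Data collection will be done preoperatively, intraoperatively, 3-6 weeks postoperatively and at 12 weeks postoperatively 1 year and up to two year". The Procedures paragraph adds: "Standard of care office visits with clinical and xray evaluations will be conducted at 3-6weeks, 3 months and beyond". At 3 months the app already asks each patient about pain, narcotic use, assistive device, sleep and knee function.

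On loss, the plan accepts that "Some participants will not return for follow-up at the required intervals", and the sample size is set "assuming a 10% drop out rate". The tracing procedure aims "to urge participants to return for clinic follow-up or ascertain if a participant has moved, died, or otherwise become lost to follow-up".

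The plan gives no complication definition, no denominator, no rule for patients without 3-month follow-up, and no account of how complications were recorded in the historical manual cohort.

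**The concern.** A hospital record holds what was treated in that system or reported to its staff. A wound problem, clot, infection or reoperation handled at another hospital reaches EPIC only if the patient mentions it at a visit and someone charts it. For a patient who does not come back, even that route is closed. An event missed in this way can only lower the recorded count.

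The protocol says the study should bring out disadvantages of robotic TKA as well as advantages, and tell patients what outcomes to expect. These four rows carry most of that burden after discharge. Few events are likely among about 95 patients, so one or two missed events would visibly change the reported percentage. The patient is already being questioned at the same time point, so the gap is avoidable.

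**Working it through.** **The plan's own figures.** The plan states no complication rate, so there is none to reproduce. The only relevant figure is the dropout allowance: "assuming a 10% drop out rate, we will enroll 95 patients with a goal of achieving 86 patients to match the historical cohort". This reproduces as 86 × 1.10 = 94.6, rounded up to 95. Dividing instead gives 86 / 0.90 = 95.6, or 96. The one-patient difference does not matter here.

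**Inputs for the illustration.** From the plan: 95 enrolled and roughly 10% not completing. Assumed: 10 patients with no 3-month record, 85 followed, a true risk of 5% in those followed, and a risk k times as high in those lost, with k = 1, 2 or 3.

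**Step 1, events.**
- Recorded events = 85 × 0.05 = 4.25.
- True events = 4.25 + 10 × 0.05 × k = 4.75, 5.25 or 5.75.
- Missed events = 0.5, 1.0 or 1.5.
- True rate over 95 = 5.0%, 5.5% or 6.1%.

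**Step 2, shortfall in the reported rate under two denominators.**

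| k | True rate | Recorded, divided by 95 | Shortfall | Recorded, divided by 85 | Shortfall |
|---|---|---|---|---|---|
| 1 | 5.0% | 4.5% | 11% | 5.0% | 0% |
| 2 | 5.5% | 4.5% | 19% | 5.0% | 10% |
| 3 | 6.1% | 4.5% | 26% | 5.0% | 17% |

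Shortfall = 1 − recorded rate / true rate. For example, 1 − 4.25/5.75 = 26% with 95 as denominator, and 1 − 5.0/6.05 = 17% with 85. The 11% floor in the first set comes entirely from keeping lost patients in the denominator as event-free.

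**Step 3, events treated elsewhere.** Steps 1 and 2 assume that every event among the 85 is charted. Let q be the share of events treated elsewhere and never charted (assumed 0 to 30%; the documents give no value), and let l = 10% be lost, at the same risk as the rest.
- Lost patients kept as event-free: shortfall = 1 − (1 − l)(1 − q), which is 1 − 0.9 × 1.0 = 10% to 1 − 0.9 × 0.7 = 37%.
- Lost patients removed: shortfall = q, so 0% to 30%.

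**Step 4, sampling error.** The exact 95% interval for 4 events in 95 is 1.2% to 10.4%. The whole span from 4.5% to 6.1% lies inside it.

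**The case against.** The strongest reply is that EPIC is not an alternative to seeing the patient. Visits at 3-6 weeks and 3 months would ordinarily be charted there, and an outside event can be reported and entered. This stands: what is missing is a specified question, and a reader who infers that patients will never be asked goes beyond the text.

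Three other readings are tempting and also go too far.
- *Missing entries count as no event, so the rates are understated.* No section gives a coding rule or divides by everyone enrolled. Understatement is a risk, not a demonstrated fact.
- *Nothing is collected in the 3-6 week window.* Table 4 spans those weeks, with one-month items, and the postoperative EOS image may be taken at that visit. Only a complication item is absent.
- *The comparison favours the robot.* How the manual cohort's complications were recorded is not described. Similar methods would give similar under-counting, and different methods could bias either way.

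The 10% is also an allowance for the app-based pain endpoint. A patient who stops using the app may still attend clinic and have a full record, and tracing is intensive: at least 10 calls, several letters and a death-index check. That weakens 10 unrecorded patients as an estimate. It does not close the gap, because the procedure specifies no complication question even when contact succeeds.

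Finally, the DVT/PE cell may be a clerical or table-extraction slip. That point and the unstated denominator would be minor on their own.

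**Conclusion.** The concern holds as a risk of under-counting. Three of the four complication rows depend on EPIC alone, the fourth has no usable source, and no planned item asks the patient about care elsewhere. The absolute robotic rate may therefore be too low.

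The amount cannot be determined from the documents. The illustrative shortfall is 0% to 26%, about half an event to one and a half events. It rests on an assumed 5% risk, 10 of 95 patients unrecorded, one to three times the risk in those lost, and either denominator. Uncharted outside events among patients who do return would add to it. Nothing can be said about the direction of bias in the comparison with manual TKA.

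Importance is limited. Complications are in neither hypothesis, no test of them is planned, and the pain endpoint is untouched. This is a cheap improvement to a secondary, descriptive outcome.

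**What to change.** 1. Add brief yes/no questions with dates (wound problem, clot, infection, further operation, each treated anywhere) to the 3-6 week visit, the 3-month app survey and any successful lost-to-follow-up contact. Confirm positive answers from records.
2. In Table 5, name EPIC plus patient report as the source for all four rows, including DVT/PE.
3. Report rates among patients with a documented 3-month contact, and show the number without one as unknown.
4. Compare with the manual cohort only on a definition available in both. EPIC-only serves if the historical study used it. Otherwise report the robotic rate descriptively, without a comparison.

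The cost is a few extra questions in contacts already planned, some record checking, a possibly less favourable robotic rate, and a second definition to report. The fuller robotic count should be labelled as not comparable with the manual cohort. Step 3 does not remove bias if those lost have a higher risk (10% and 17% at two and three times the risk in the illustration), which is why the unknowns must be shown.
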